9.4.5.1 Anti-somapacitan antibodies

Determination of antibodies against somapacitan in subjects randomised to somapacitan will be performed by a special laboratory using a validated antibody assay. Confirmed anti-somapacitan

Protocol
Trial ID: NN8640-4245
UTN: U1111-1207-9741
Eudract Number: 2018-000232-10

~~CONFIDENTIAL~~

Date:
Version:
Status:
Page:

12 June 2020
7.0
Final
47 of 102

Novo Nordisk

antibody positive samples will be further tested for cross-reactivity to hGH and for in vitro neutralising effect in a validated neutralising antibody assay and by correlation to PK/PD.

9.4.5.2 Anti-hGH antibodies

Anti-hGH antibodies in subjects randomised to Norditropin® will be analysed by a special laboratory using a validated antibody assay. Confirmed anti-hGH antibodies will be further assessed for in vitro neutralising effect of anti-hGH antibodies in a validated neutralising antibody assay and by correlating to PK/PD.

9.4.5.3 Assessment in case of suspicion of severe systemic hypersensitivity

In the event of a severe local and/or systemic hypersensitivity reaction possible or probably related to trial product, blood sampling for assessment of anti-somapacitan or anti-Norditropin® IgE antibodies as well as binding antibodies should be performed in relation to the reaction and no later than 1-2 weeks after the event.

In the event of a severe systemic hypersensitivity reaction to trial product it is recommended also to analyse a sample collected within 3 hours of the reaction for tryptase (total and/or mature tryptase) at the local laboratory. Moreover, a baseline tryptase measurement is necessary 1-2 weeks after the immediate severe hypersensitivity reaction due to individual variation in tryptase baseline concentration.

A follow up visit should be conducted 3-4 weeks after the allergic reaction with repeated blood sampling for assessment of anti-somapacitan or anti-Norditropin® IgE antibodies as well as binding antibodies and, if possible, also at a visit 3 months post the hypersensitivity reaction for assessing the persistence of the IgE response. Tryptase measurements are not required at the follow up visits.

9.5 Pharmacokinetics

Samples will be used to evaluate the PK of somapacitan and Norditropin®.

All samples must be drawn prior to trial product administration if this is planned on a sampling day. The bioanalysis of somapacitan and Norditropin® PK samples will be performed by a special laboratory.

9.6 Pharmacodynamics

IGF-I and IGFBP-3 will be used to evaluate the PD of somapacitan and Norditropin®. CCI [REDACTED]

[REDACTED]
[REDACTED].

9.7 CCI [REDACTED]

CCI [REDACTED]

Protocol
Trial ID: NN8640-4245
UTN: U1111-1207-9741
Eudract Number: 2018-000232-10

~~CONFIDENTIAL~~

Date:
Version:
Status:
Page:

12 June 2020
7.0
Final
48 of 102

Novo Nordisk

CCI

9.8 Biomarkers

Not applicable for this trial

10 Statistical considerations

10.1 Sample size determination

The trial will have 5 treatment arms with a total of 60 subjects randomised using a 1:1:1:1:1 randomisation ratio. The primary endpoint is assessed 26 weeks after randomisation. At this time point few or no trial participants are expected to be withdrawn based on data from NN8640-4172, a phase 2 trial (smapacitan) in children with GHD. Assuming 55 subjects are available in total (11 subjects per treatment arm) and a SD of 2.6 cm/year for annualised HV after 26 weeks of treatment (SD value based on data from hgh-1424, a phase 3 trial²³ (daily hGH) in children born SGA), the trial should have a probability of 80% to detect a difference between two specific treatment arms if the true difference between the two treatments is at least 3.25 cm/year. The power of the trial for 3 SD scenarios is:

True difference	SD		
	2.4 cm/year	2.6 cm/year	2.8 cm/year
3.0 cm/year	80%	73%	67%
3.25 cm/year	85%	80%	74%
3.5 cm/year	90%	85%	80%

10.2 Definition of analysis sets

The Full analysis set (FAS) is defined as all randomised subjects exposed to the trial product. Exclusion of data from analyses should be used restrictively, and normally no data should be excluded from the FAS. The subjects or observations to be excluded, and the reasons for their exclusion must be documented before database lock (DBL). The subjects and observations excluded from analysis sets, and the reason for this, will be described in the CTR. Subjects will be analysed “as treated”.

The Safety analysis set (SAS) is defined as all randomised subjects exposed to trial product. Subjects will be analysed “as treated”.

The Per Protocol (PP) analysis set is defined as subjects from FAS who have not violated any inclusion/exclusion criteria and have used the randomised treatment for at least 22 weeks (for subjects receiving somapacitan) or 154 days (for subjects receiving Norditropin®). Subjects will be analysed “as treated”.

All efficacy endpoints will be analysed using FAS and all safety endpoints will be analysed using SAS.

Protocol
Trial ID: NN8640-4245
UTN: U1111-1207-9741
EudraCT Number: 2018-000232-10~~CONFIDENTIAL~~Date:
Version:
Status:
Page:12 June 2020
7.0
Final
50 of 102**Novo Nordisk**

Two observation periods are defined,

- on-treatment: from first administration and up until last trial contact, visit 6 or 14 days after last administration, whichever comes first
- in-trial: from first administration and up until visit 6 or last trial contact, whichever comes first

The observation periods for the extension I part of the trial are defined analogously by exchanging “visit 6” in the definitions above with “Follow-up visit 25” for subjects who do not continue in extension II or “visit 8” for subjects continuing in extension II.

For the on-treatment observation period of the extension II part of the trial, “visit 6” in the on-treatment observation period definition above is exchanged with visit 24 or visit 24A for subjects who do not attend visit 24. The in-trial observation period for the extension II part of the trial is defined analogously by exchanging “visit 6” in the definition above with “Follow-up visit 25”.

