10.3.1 Primary endpoint

Endpoint title	Time frame	Unit
HV	From baseline (week 0) to visit 6 (week 26)	cm/year

Height is measured at baseline and 26 weeks and the primary endpoint is derived as:

$HV = (\text{height at 26 weeks visit} - \text{height at baseline}) / (\text{time from baseline to 26 weeks visit in years})$.

Annualised HV at 13 weeks, 39 weeks and 52 weeks will be derived analogously to the primary endpoint : $(\text{height at } d \text{ weeks visit} - \text{height at baseline}) / (\text{time from baseline to } d \text{ weeks visit in years})$, where $d=13,39,52$.

The primary objective is to evaluate the effect of somapacitan vs Norditropin® on longitudinal growth in children with short stature born SGA with no catch-up growth by 2 years of age or older and the primary analysis of the primary endpoint is the main tool for achieving this. Conclusions from the primary analysis will be based on CIs for the specified treatment differences and not on hypothesis testing.

Protocol
Trial ID: NN8640-4245
UTN: U1111-1207-9741
EudraCT Number: 2018-000232-10

~~CONFIDENTIAL~~

Date:
Version:
Status:
Page:

12 June 2020
7.0
Final
51 of 102

Novo Nordisk

The primary analysis of the primary endpoint is based on FAS and the 'in-trial' observation period.

Annualised HV at 13 and 26 weeks will be analysed using a mixed model for repeated measurements (MMRM) with treatment, age group, sex, region and sex by age group interaction term as factors and height at baseline as a covariate, all nested within week as a factor. An unstructured covariance matrix will be used to describe variability for the repeated measurements for a subject. From the model the treatment differences at week 26: somapacitan 0.24 mg/kg/week vs Norditropin® CCI █ mg/kg/day, somapacitan 0.20 mg/kg/week vs Norditropin® CCI █ mg/kg/day, somapacitan 0.20 mg/kg/week vs Norditropin® CCI █ mg/kg/day, and somapacitan 0.16 mg/kg/week vs Norditropin® CCI █ mg/kg/day will be estimated with the corresponding 95% CI. Subjects without post-randomisation HV data will not be included in the primary analysis. Data from subjects who have discontinued randomised treatment before week 26 will be used in the primary analysis.

The analysis will be repeated on the PP analysis set as a sensitivity analysis.

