10.3.5 Other analyses

Annualized HV at 13 weeks, 26 weeks, 39 weeks and 52 weeks will be analysed using a MMRM with treatment, age group, sex, region and sex by age group interaction term as factors and height at baseline as a covariate, all nested within week as a factor. An unstructured covariance matrix will be used to describe the variability for the repeated measurements for a subject. From the MMRM the treatment differences at week 52 weeks will be estimated for the same treatment contrasts as for the primary analysis of the primary endpoint.

Height profiles will be presented by subject with time point for treatment switch in the extension II period (if applicable) and start of puberty (if applicable) indicated in the graphs. Annualised HV for the second year in trial will be derived as: (height at 104 weeks visit – height at 52 weeks visit) / (time from 52 weeks visit to 104 weeks visit in years). Annualised HV for the second year in trial will be analysed using descriptive statistics by treatment arm (treatment arm from main trial period), as well as by extension II period treatment arm. Annualised HV for third, fourth and fifth year in trial will be derived analogously and analysed using descriptive statistics.

Change in height SDS, HV SDS, IGF-I SDS and IGFBP-3 SDS from baseline to week 52 will be analysed using an MMRM on available assessments from planned visits similar to the MMRM used for the analysis of week 26 data, with baseline assessment as covariate and treatment, age group, sex, region and sex by age group interaction term as factors, all nested within week as a factor.

IGF-I SDS and IGFBP-3 SDS data from extension II will be analysed using descriptive statistics.

Protocol
Trial ID: NN8640-4245
UTN: U1111-1207-9741
EudraCT Number: 2018-000232-10~~CONFIDENTIAL~~Date:
Version:
Status:
Page:12 June 2020
7.0
Final
54 of 102**Novo Nordisk**

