
 • Important medical event: 
 • Medical or scientific judgment should be exercised in deciding whether SAE reporting is appropriate in other situations. This includes important medical events that may not be immediately life-threatening or result in death or hospitalisation, but may jeopardise the subject or may require medical or surgical intervention to prevent one of the other outcomes listed in the above definition. These events should usually be considered serious and reported as SAEs using the important medical event criterion. 
 • The following adverse events must always be reported as SAEs using the important medical event criterion, if no other seriousness criteria are applicable: 
 ▪ suspicion of transmission of infectious agents via the trial product. ▪ risk of liver injury defined as alanine aminotransferase (ALT) or aspartate aminotransferase (AST) $>3 \times$ UNL and total bilirubin $>2 \times$ UNL, where no alternative aetiology exists (Hy's law).

Description of AEs requiring additional data collection (via specific event form)**Injection site reactions:**

An injection site reaction is defined as: An injection site reaction considered clinically significant by the investigator. An injection site reaction form should be filled in, in addition to the AE form (and safety information form (SIF) for SAE).

In addition digital photos should be taken of the injection site reaction at the time of identification and hereafter as frequent as judged by the investigator. The photos will be evaluated by an external dermatologist and subsequently transferred to Novo Nordisk.

The overall process for photo acquisition, central analysis, transfer of photos reporting of results and archiving will be described in a manual prepared by the vendor performing the dermatology review.

Medication error:

A medication error is an unintended failure in the trial drug treatment process that leads to, or has the potential to lead to, harm to the subject such as:

- Administration of wrong drug or use of wrong device.

Protocol
Trial ID: NN8640-4245
UTN: U1111-1207-9741
EudraCT Number: 2018-000232-10~~CONFIDENTIAL~~Date: 12 June 2020 | **Novo Nordisk**
Version: 7.0
Status: Final
Page: 77 of 102

- Note: Use of wrong DUN is not considered a medication error unless it results in a confirmed administration of wrong drug.

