- Wrong route of administration, such as intramuscular instead of subcutaneous.
- Accidental administration of a higher dose than intended; the administered dose must deviate from the intended dose to an extent where clinical consequences for the trial subject were likely to happen as judged by the investigator, although they did not necessarily occur.

AE and SAE recording

- The investigator will record all relevant AE/SAE information in the CRF.
- The investigator will attempt to establish a diagnosis of the event based on signs, symptoms, and/or other clinical information. In such cases, the diagnosis (not the individual signs/symptoms) will be documented as the AE/SAE.
- When an AE/SAE occurs, it is the responsibility of the investigator to review all documentation (e.g. hospital progress notes, laboratory and diagnostics reports) related to the event.
- For all non-serious AEs the applicable forms should be signed when the event is resolved or at the end of the trial at the latest. For sign-off of SAE related forms refer to “SAE reporting via paper CRF” later in this section.
- Novo Nordisk products used as concomitant medication: if an AE is considered to have a causal relationship with a Novo Nordisk marketed product used as concomitant medication in the trial, it is important that the suspected relationship is reported to Novo Nordisk, e.g. in the alternative aetiology section on the safety information form. Novo Nordisk may need to report this adverse event to relevant regulatory authorities.

Assessment of severity

The investigator will assess intensity for each event reported during the trial and assign it to one of the following categories:

- **Mild:** An event that is easily tolerated by the subject, causing minimal discomfort and not interfering with everyday activities.
- **Moderate:** An event that causes sufficient discomfort and interferes with normal everyday activities.
- **Severe:** An event that prevents normal everyday activities.
- Note: Severe is a category used for rating the intensity of an event; and both an AE and SAE can be assessed as severe. An event is defined as ‘serious’ when it meets at least one of the outcomes described in the definition of an SAE and not when it is rated as severe.

Assessment of causality

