Date of Birth will be recorded only as year of birth. Race and ethnicity will not be collected.

Only applicable for Switzerland:

The trial will be conducted in compliance with Therapeutic Products Act of 15 December 2000 (Status as of 1 January 2018) (TPA/HMG) and Ordinance on clinical trials in Human Research (HRO/KlinV) of 20 September 2013 Status as of 1 January 2018.

Date of birth will be collected as year of birth.

Only applicable for US:

Clarification of physical examination: A fundoscopic exam should be performed at baseline and according to local practice.

CCI

CCI

mg/kg/day CCI

CCI

CCI

mg/kg/day.

The US subjects who are randomised to Norditropin® CCI mg/kg/day and enter puberty during the main phase will be switched to Norditropin® CCI mg/kg/day after the assessment of primary endpoint data has been completed.

Only applicable for France:

A specific indemnity statement is required: The French Public Health Code article L 1121-10 (law n° 2004-806 of 9 August 2004 art. 88 I, IX Journal Officiel of 11 August 2004. "The sponsor is responsible for identification of the harmful consequences of the biomedical research for the person lending himself thereto and for indemnification of his beneficiaries, except in case of proof, incumbent on it, that the prejudice is not attributable to his fault or the fault of any intervening party, without the sponsor's being entitled to call on acts by a third party or the voluntary withdrawal of the person who had initially consented to cooperating in the research.

Protocol
Trial ID: NN8640-4245
UTN: U1111-1207-9741
EudraCT Number: 2018-000232-10

~~CONFIDENTIAL~~

Date: 12 June 2020 | **Novo Nordisk**
Version: 7.0
Status: Final
Page: 91 of 102

Race and ethnicity will not be collected.

Exclusion criterion 13. Any disorder which, in the opinion of the investigator, might jeopardise subject's safety or compliance with the protocol and patients having contraindication to start treatment with Norditropin®.

Dose modification. Data from an interaction study performed in GH deficient adults suggests that GH administration may increase the clearance of compounds known to be metabolized by cytochrome P450 isoenzymes. The clearance of compounds metabolized by cytochrome P450 3A4 (e.g. sex steroids, corticosteroids, anticonvulsants and cyclosporine) may be especially increased resulting in lower plasma levels of these compounds. The clinical significance of this is unknown.

[figure not shown]

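### The full analysis set, which carries the primary and all other efficacy analyses, is grouped as treated rather than as randomised; the term is not defined and no as-randomised efficacy analysis is planned

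*Combined protocol and SAP*

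**What the plan says.** Section 10.2 defines three analysis sets and gives all three the same grouping rule. For the FAS (everyone randomised who received trial product) the definition ends: "will be described in the CTR. Subjects will be analysed “as treated". The safety set has the same membership and the same rule. The per-protocol (PP) set takes FAS children with no eligibility violation and at least 22 weeks or 154 days on the randomised product, again grouped as treated.

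The section then says: "All efficacy endpoints will be analysed using FAS and all safety endpoints will be analysed using SAS". Section 10.3.1 repeats this for height velocity: "The primary analysis of the primary endpoint is based on FAS". The one sensitivity analysis is: "The analysis will be repeated on the PP analysis set as a sensitivity analysis". For week 52, section 10.3.5 says "the treatment differences at week 52 weeks will be estimated for the same treatment contrasts as for the primary analysis" of the primary endpoint.

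No section says whether *as treated* refers to the product, the starting dose or the dose actually received. Section 4.2 marks estimands as not applicable, so it does not settle the matter either.

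**The concern.** As-treated grouping is the usual choice for safety. For efficacy, the comparison that randomisation protects is the one between the groups as assigned. Section 5.4 relies on stratified randomisation to balance the five arms, and regrouping children by what they received gives up part of that balance.

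The documents show several ways in which received and assigned treatment could differ, or in which the arm label is unclear:

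- **Medication errors.** Appendix 4 lists "Administration of wrong drug or use of wrong device" and "Accidental administration of a higher dose than intended" among the reportable errors.
- **Discontinuation followed by marketed growth hormone.** Sections 7.7.1 and 7.8 allow it, section 8.1 asks these children to keep attending, and 10.3.1 keeps their data in the primary analysis. No sentence says in which arm they count.
- **The US switch in Appendix 9.** US children on one Norditropin dose who "enter puberty during the main phase will be switched to" another stated Norditropin dose change after the primary endpoint has been assessed. Only week-52 analyses (bone age and the height velocity contrasts) can be affected. Puberty itself affects growth, so the label matters there. The doses are redacted, so it cannot be checked whether the new dose is that of the other control arm.
- **Dose reduction under 7.2.1.** This moves a child only if *as treated* is read as dose received. The text neither says so nor rules it out.

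The primary estimates bear on the trial's main decision: under 5.1 and 5.5 the main-period data inform the somapacitan dose for the 208-week extension II.

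**Working it through.** **Inputs.** From section 10.1: 11 evaluable children per arm, SD 2.6 cm/year (alternatives 2.4 and 2.8), 80% power at a difference of 3.25 cm/year. From section 10.3: two-sided 5% level. Assumed, because the documents give no figure: the number of relabelled children and how far they lie from their arm's mean.

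**The plan's own figure.** Standard error of a two-arm contrast = 2.6 × √(2/11) = 1.109 cm/year. A two-sample t-test with 20 degrees of freedom at 3.25 cm/year has 79.6% power, matching the stated 80%. The other eight cells of the power table also reproduce within one percentage point. These figures do not depend on the grouping rule.

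**Precision of a contrast.** 95% CI half-width = 2.086 × 1.109 = 2.31 (df 20), or 2.009 × 1.109 = 2.23 (df 50, all five arms pooled).

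**Shift from relabelling, one arm of the contrast affected.** With *k* children each lying *g* above the mean of an arm of *n*:

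- taking them out lowers that arm's mean by *kg*/(*n* − *k*);
- adding them raises it by *kg*/(*n* + *k*).

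| Children moved | Deviation | SD (cm/year) | Out of the arm | Into the arm |
|---|---|---|---|---|
| 1 | +1 SD | 2.6 | 2.6/10 = 0.26 (0.23 SE) | 2.6/12 = 0.22 (0.20 SE) |
| 2 | +1 SD | 2.6 | 5.2/9 = 0.58 (0.52 SE) | 5.2/13 = 0.40 (0.36 SE) |
| 1 | +0.5 SD | 2.6 | 1.3/10 = 0.13 | 1.3/12 = 0.11 |
| 1 | +2 SD | 2.6 | 5.2/10 = 0.52 | 5.2/12 = 0.43 |
| 1 | +1 SD | 2.4 | 2.4/10 = 0.24 | 2.4/12 = 0.20 |
| 1 | +1 SD | 2.8 | 2.8/10 = 0.28 | 2.8/12 = 0.23 |

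**Shift when the child moves between the two arms of one contrast.** The two effects add. One child at +1 SD, no true treatment difference: 2.6/10 + 2.6/12 = 0.48 cm/year. With all 12 randomised per arm: 2.6/11 + 2.6/13 = 0.44. Two children, 11 per arm: 5.2/9 + 5.2/13 = 0.98. A child below the mean gives the same shift with the opposite sign.

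**No relabelled child.** The shift is zero and the two groupings coincide.

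**The case against.** The strongest reply is that the rule will rarely matter here.

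- Assignment is central through the IWRS and pens are accounted for by dispensing unit. The two products differ in pen and in schedule, so a sustained mix-up is unlikely. An isolated dosing error need not change anyone's arm.
- The familiar harm of as-treated efficacy analyses, losing children who stop treatment, is largely absent, because the primary analysis retains their data and section 10.2 restricts exclusions.
- PP membership requires use of the randomised product, so labels in that set should almost always match randomisation.
- The US switch comes too late for the primary endpoint, and the natural reading of extension I as the same five-arm design keeps the original arms.
- The trial is exploratory, concludes from confidence intervals and has age group, sex and region in the model.

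Most of this stands, and it limits the size of the problem. It does not remove it. The PP set is selected on eligibility and on exposure after randomisation, so it may help expose an influential mix-up but cannot replace the randomised comparison. The natural reading at week 52 is not written down. If mix-ups really are rare, as-randomised grouping gives up almost nothing.

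One further point is fair: as-randomised grouping dilutes a real effect when a child takes the other arm's treatment throughout. With one such child in 11, a true 3.25 cm/year becomes 3.25 × 10/11 = 2.95. That is the accepted price of an unbiased comparison of assigned groups, and an as-treated analysis can be shown beside it.

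**Conclusion.** The point holds. This is a stated rule that departs from the randomised comparison, not merely a detail left out. It covers the primary endpoint and every other FAS efficacy analysis, it rests on an undefined term, and no planned full-set analysis shows the alternative.

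The likely consequence is modest. One relabelled child at an assumed 1 SD moves a contrast by roughly a tenth of its CI half-width if one arm is affected and by about a fifth if both are. The true number of such children is unknown and may be none. The finding on wording is firm; its numerical effect depends on those assumptions. It rests on section 10 of the document, which contains no separate SAP text that might define the term. The point is worth correcting because arms of about 12 make each child count and because the rule should be fixed before the main-period data are unblinded.

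**What to change.** In section 10.2:

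1. Replace the grouping sentence in the FAS definition with one stating that subjects are analysed as randomised.
2. Keep *as treated* for the safety set, and for the PP set if wanted, and define it there: by product, starting dose or dose received, and how a mixed exposure is classified.
3. State that permitted dose modifications, a move to marketed growth hormone after discontinuation, and the Appendix 9 switch do not change a child's arm in efficacy analyses, including those at week 52.

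Section 10.3.5 already ties second-year height velocity to the main-period arm. It is only a loose precedent, since it does not say whether that arm is the assigned or the received one; the same clarification should be added there.

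The cost is two or three sentences of protocol text, plus that short clarification. No extra data, visits or children are needed, and the planned power calculation (about 80% at 3.25 cm/year with 11 per arm) is unchanged.
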